3.5. Effectiveness Objective

3.5.1. Endpoints

The primary endpoint is as follows:

1. Overall and heart failure related healthcare costs of care between subjects treated with the Furoscix Infusor 30 days post discharge from the emergency department compared to propensity score versus matched controls treated in the hospital for \leq 72 hours through 30 days post discharge

The primary analysis is to compare the Furoscix Infusor (prospective arm) versus treatment as usual (historical control arm) with respect to overall cost of care and total HF-related costs. Comparison of these data between the matched (paired) cohorts will be conducted via a t-test or a Wilcoxon signed-rank test depending on the distribution of the data.

Secondary endpoints are as follows:

1. Number of hospital admissions and duration with-in 30 days post discharge from the emergency department
2. Number of HF-related hospital admissions and duration with-in 30 days post discharge from the emergency department
3. Number of HF-related emergency department visits with-in 30 days post discharge from the emergency department
4. Number of HF-related clinic visits with-in 30 days post discharge from the emergency department
5. Description of health-related quality of life using the twelve-item Kansas City Cardiomyopathy Questionnaire (KCCQ-12, for Furoscix Infusor cohort only), administered on Day 0 and Day 30.
6. Change in NT-proBNP (for Furoscix Infusor cohort only)
7. Subject and/or caregiver satisfaction with Furoscix Infusor (for Furoscix Infusor cohort only)

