8. STATISTICS

8.1. Determination of Sample Size

Based on an average hospital cost of a patient hospitalized for \leq 72 hours with a primary diagnosis of HF (Diagnosis Related Group Code 291, 292 and 293) of \$8,600 (standard deviation: \$3,045), 68 patients (34 in each group) are required to have an 80% chance of detecting a decrease in hospital costs to \$6,500 at a significance level of 5%. The target sample size of the Furoscix cohort will initially be N=34 subjects.

Given the anticipated overdispersion of the primary outcome (i.e., difference in total HF-attributable direct medical costs), we will employ adaptive trial design procedures for sample size re-estimation. This adaptive-total information criterion approach was taken due to the risk of incorrectly estimating the sample size due to misspecification of the cost outcome parameters. By using the adaptive sample size design, which includes no penalty for repeated interim analysis, the final sample size will be sufficient to provide adequate power to test the stated hypothesis.

This will include re-assessment of the sample size at N=34 in the Furoscix cohort by using a group sequential design and testing to allow for stopping. It is not expected that the sample size for the Furoscix Infusor arm would exceed N=75, but the maximum value cannot be definitively stated until the analysis at N=34 is completed.

We will explore ratios ranging from 1:1 to 4:1 for the number of historical controls to be matched to Furoscix-treated patients using methods reported by Millar and Pasta 2010. The simulations will be used to find the matching ratio at which the level of precision is optimized without biasing the variance of the outcome measure. Additional methodological details are described in the prespecified statistical analysis plan.

The methodology by which the sample size will be re-estimated and stopping rules will be implemented will be detailed in the statistical analysis plan.

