8.3.1. Primary Endpoint

The primary endpoint analysis will compare the difference in the overall and heart failure related healthcare costs between subjects treated with the Furoscix Infusor 30 days post discharge from the emergency department for worsening heart failure due to fluid overload with propensity score matched controls treated in the hospital for \leq 72 hours through 30 days post discharge. Propensity scoring methods will be described in the statistical analysis plan. Comparison of these data between the matched (paired) cohorts will be conducted via a t-test or a Wilcoxon signed-rank test depending on distribution of data.

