3.3.3. P-Values

The statistical test for the primary objective will be performed at two-sided $\alpha=0.05$. All reported p-values ≥ 0.0001 will be rounded to four decimal places. P-values <0.0001 will be displayed as “ <0.0001 ”.

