3.3.5. Trial Design

A group sequential design is being employed to allow for stopping due to futility or efficacy. This design includes the following general steps (cite SAS manual for group sequential designs):

1. Specify the statistical details of the design, including the null and alternative hypotheses (null hypothesis being that there is no difference in 30-day HF-related direct medical costs between the Furoscix Infusor and historical control arms), a test statistic for the hypothesis test, the Type I and II error probabilities, a stopping criterion, the total number of stages, and the relative information level at each stage.
2. Compute the boundary values for the trial based on the specifications in Step 1 and compute the sample size required at each stage for the specified hypothesis test.
3. At each stage, collect additional data with the required sample sizes. This includes the data collected at the current stage in addition to the data collected at previous stages.
4. At each stage, analyze the available data and compute the test statistic.
5. At each stage, compare the test statistic with the corresponding boundary values. The trial will stop to reject or accept the hypothesis, or it will continue to the next stage.
6. Once the trial stops, parameter estimates, confidence limits for the parameter, and a p-value for the hypothesis test are computed.

Below is a depiction of a hypothetical 4-stage design with two-sided testing.

Figure 1. Boundaries for Two-Sided Group Sequential Test

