3.5.2. Step 1: Determining the Initial Target Sample Size

Although this is an adaptive clinical trial with sequential cohort design whereby the final sample size will ultimately be determined by the prespecified interim analyses, it was necessary for trial planning purposes to generate an estimated final sample size based purely on a priori assumptions.

Based on an average hospital cost of a patient hospitalized for \leq 72 hours with a primary diagnosis of HF (Diagnosis Related Group Code 291, 292 and 293) of \$8,600 (standard deviation: \$3,045), 68 patients (34 evaluable patients in each group) are required to have an 80% chance of detecting a decrease in hospital costs to \$6,500 at a significance level of 5%. The target sample size of the Furoscix cohort will initially be N=34 subjects.

Re-assessment of the sample size will be conducted once 34 subjects in the Furoscix cohort complete all study phases as per protocol (matched 1:1 to 4:1 to propensity matched controls to generate comparisons) by using a group sequential design and testing to allow for stopping. It is not expected that the sample size for the Furoscix Infusor arm would exceed N=75, but the maximum value cannot be definitively stated until the analysis at N=34 is completed.

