3.5.4. Step 3: Compute Boundary Values for Primary Outcome

Boundary values for the primary outcome will be derived via the SEQDESIGN (REF SAS SEQDESIGN) procedure in SAS; specifically using a two-sided O’Brien Fleming design which has conservative stopping boundary values at early stages, and boundary values at the final stage that are close to the fixed-sample design. This produces a conservative design because compared to other approaches, the O’Brien-Fleming approach makes it more difficult to reject the null hypothesis in early stages than in later stages (null hypothesis being that there is no difference in 30-day HF-related direct medical costs between the Furoscix Infusor and historical control arms).

Assume that the total 30-day HF-related direct medical costs are normally distributed with means μ_e and μ_c for individuals in the Furoscix Infusor and historical control groups, respectively. The null hypothesis of no effect for the Furoscix Infusor is $H_0 : \theta = 0$, where $\theta = \mu_e - \mu_c$

The specific procedure for determining the boundary values for the primary outcome are specified elsewhere (REF SAS SEQDESIGN). Utilizing this procedure requires that we prespecify the meaningful difference between groups and the standard deviation thereof in order to achieve the specified power. The boundary values will be estimated based on a difference of \$2,100 (based an average hospital cost of a patient hospitalized for ≤ 72 hours with a primary diagnosis of HF (Diagnosis Related Group Code 291, 292 and 293) of \$8,600 (standard deviation: \$3,045), 68 patients (34 in each group) are required to have an 80% chance of detecting a decrease in hospital costs to \$6,500 at a significance level of 5%).

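### Two costs are named as primary, but the hypothesis, stopping boundaries and single 5% test cover one cost, and no rule says which result decides success

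*SAP*

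**What the plan says.** **Two costs are primary.** SAP 3.5.1 sets the primary comparison of the arms "with respect to overall cost of care and total HF-related costs". SAP section 3 names the same pair. Protocol 8.3.1 says the analysis will "compare the difference in the overall and heart failure related healthcare costs between subjects treated with the Furoscix Infusor" and matched controls; the synopsis (endpoints and statistical analysis), 3.2.1 and 6.1.1 agree. SAP 3.5.3.1 defines the two separately: overall cost takes in all-cause resource use, while HF-related cost takes in use with a primary HF diagnosis.

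**One cost carries the inference.** The null hypothesis in SAP 3.3.5 is that "there is no difference in 30-day HF-related direct medical costs between the Furoscix Infusor and historical control arms". SAP 3.5.4 repeats it and builds the boundary model on HF-related cost only. Protocol 8.1, like the synopsis, describes "the primary outcome (i.e., difference in total HF-attributable direct medical costs". SAP 3.3.3 is in the singular: "The statistical test for the primary objective will be performed at two-sided" 0.05.

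**One difference is sized.** SAP 3.5.2 says that 34 evaluable patients per group "are required to have an 80% chance of detecting a decrease in hospital costs" from $8,600 (SD $3,045) to $6,500. In SAP 3.5.4, "The boundary values will be estimated based on a difference of" $2,100, which is the same figure.

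**Multiplicity.** SAP 3.3.5 spends type I error over the interim and final looks. Neither document gives an order, an alpha split, a both-must-succeed rule or an either-suffices rule for the two costs.

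**The concern.** The passages disagree on what the primary test is. The endpoint text gives two comparisons and the inferential text gives one. A reader cannot tell what would count as success if the costs disagreed.

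This also affects conduct. SAP 3.5.5 plans looks for efficacy and futility at N=10 and N=34, with more as needed, and protocol 5.10 stops on a confidence-interval width for the primary endpoint. Neither says which cost governs. The study is unblinded (protocol 5.6), so a rule left open now could be chosen with results in view. The possible consequences are an error rate above 5% under one reading and power below 80% under another.

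**Working it through.** **1. The plan's own figure.** Inputs from SAP 3.5.2: difference $2,100, SD $3,045, 80% power, 5% level. SAP 3.3.3 gives the test as two-sided.

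n per group = 2 × [SD × (z₀.₉₇₅ + z₀.₈₀) / difference]² = 2 × [3,045 × (1.960 + 0.842) / 2,100]² = 33.005, which rounds up to 34.

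Power at 34 is 81.2% by normal approximation and 80.0% by the two-sample t. A one-sided test would need 26. The stated 34 is therefore right for one two-sided test with no allowance for a second endpoint. Its input is the hospital cost of a short HF stay, not a 30-day total of either kind.

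**2. If either cost suffices, each at two-sided 0.05.** Error rate = 1 − P(|Z₁| < 1.96 and |Z₂| < 1.96) for a bivariate normal pair. A false claim of savings counts one direction only: 1 − P(Z₁ < 1.96 and Z₂ < 1.96), taking savings as positive. The documents give no correlation, so a range is assumed.

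| Assumed correlation | Either direction | False savings claim |
|---|---|---|
| one test only | 5.0% | 2.5% |
| 0.5 | 9.1% | 4.5% |
| 0.7 | 8.3% | 4.2% |
| 0.9 | 7.0% | 3.5% |
| 0.95 | 6.5% | 3.2% |

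Independence would give 1 − 0.95² = 9.75%. That is not realistic here, because overall cost contains HF-related cost.

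**3. Effect of the looks.** O'Brien-Fleming-type spending was simulated for looks at 10/34 (boundaries |Z| of 3.62 and 1.96) and at 10/34/75 (effectively no stopping at 10, then 2.91 and 1.97). The N=75 endpoint is an assumption, taken from the size the plan does not expect to exceed. With the same boundaries applied to both costs, the either-suffices rates stay within about 0.1 percentage point of the table. One cost alone gives 5.0%. Spending over looks neither adds to the inflation nor removes it.

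If overall cost were instead tested at nominal 0.05 at every look while HF-related cost kept its boundary, the rate for correlations of 0.9 down to 0.5 would be about 11% to 13% (looks 10/34) or 14% to 16% (looks 10/34/75).

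**4. If both costs must succeed.** Assume both have the standardized effect behind the 34. Each Z then has mean 2,100 / [3,045 × √(2/34)] = 2.84. P(Z₁ > 1.96 and Z₂ > 1.96) is 70.3%, 72.8%, 76.3% and 77.7% at correlations of 0.5, 0.7, 0.9 and 0.95.

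**5. Overall cost on its own.** Nothing is sized for it. If its SD were 1.25 or 1.5 times $3,045 (assumed) with the same $2,100 difference, the mean of Z would be 2.84/1.25 = 2.27 or 2.84/1.5 = 1.90, and power at 34 would be about 62% or 47%.

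**6. Splitting alpha.** At 0.025 per cost, the formula in step 1 gives 40 per group (42 by the t-test). Staying at 34 gives 72.6% power (70.8% by t).

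**The case against.** The strongest reply is that nothing in the plan lets the sponsor win on either cost. SAP 3.3.3 speaks of one test, the only stated hypothesis is HF-related, and SAP 3.5.1 says what will be compared without defining a win. On that view HF-related cost is the sole formal test and no error is inflated. This stands in part: a reader might infer that success on whichever cost crosses is enough, and the documents do not say so. The inflation is therefore conditional. The reply does not, however, remove overall cost from the sentence that defines the primary analysis, or supply a rule.

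A reader might also infer that the interim looks compound the problem. SAP 3.5.5 sends all interim and final analyses through the sequential procedure, and step 3 shows essentially no addition when both costs use those boundaries. The 11% to 16% range needs overall cost to be tested unadjusted at each look, which no passage states. The boundaries are on the Z scale and could serve either cost; what is missing is the statement that they will.

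It is also fair to say that the two costs overlap heavily. They are summed over the same 30 days, and controls are selected on a primary-HF admission. This favours the higher correlations and so the smaller inflation. Finally, it would be too strong to say that the sample size covers HF-related cost: its input is a hospital cost, which SAP 3.5.4 carries over to the HF-related boundaries.

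**Conclusion.** The point holds as an inconsistency with a missing decision rule. Two distinct costs are primary by definition, one is primary by hypothesis and boundary, and the documents do not settle which governs.

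The size depends on the reading. If either suffices, the two-sided error is about 6.5% to 9.1%, and a false savings claim about 3.2% to 4.5% against 2.5%, for assumed correlations of 0.95 to 0.5, with the smaller figures more plausible. If both must succeed, error is controlled and power is about 70% to 78% rather than 80%, assuming equal standardized effects. If only HF-related cost is formally tested, alpha is intact, but the endpoint text must then say so.

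Confidence is high in the contradiction. The inflation itself is conditional on a rule that the plan does not state.

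**What to change.** Before the next look at outcome data:

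- Name 30-day HF-related cost as the single primary endpoint. This matches the existing hypothesis and boundaries.
- Test overall cost in fixed sequence, only if HF-related cost rejects, against its own prespecified O'Brien-Fleming boundary.
- Base the stopping decision on HF-related cost only.
- Make the change in every place that names both costs: the protocol synopsis (endpoints and statistical analysis), protocol 3.2.1, 6.1.1 and 8.3.1, and SAP 3 and 3.5.1.

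This keeps alpha at 0.05 and the target at 34. The cost is that overall cost becomes a gated key secondary endpoint with no guaranteed power, and the change needs a protocol amendment with IRB approval (protocol 9.2.2).

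If the sponsor wants both costs to remain primary, a both-must-succeed rule also controls error, provided the stated power is lowered to match. An alpha split would work too, at about 40 to 42 per group instead of 34.

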- Concomitant Medication Use in prior 3 months (90 days) of index or enrolment date (inclusive)
 - Oral Diuretic
 - Digoxin
 - ACE Inhibitors
 - Nitrates and hydralazine
 - Oral anticoagulant
 - Statin
 - Platelet Inhibitor
 - Beta Blockers
- Baseline conditions/co-morbidities in prior year (364 days) of index or enrolment date (inclusive)
 - Myocardial Infarction
 - Hypertension
 - Diabetes
 - Hyperlipidemia
 - Peripheral vascular disease
 - Arrhythmias
 - Malignancy
 - COPD
 - Stroke
 - Valvular heart disease
 - PCI
 - Acute Coronary syndrome
 - Chronic Kidney Disease Stage

- Baseline resource utilization (All-cause and HF-related) in the 6 months prior to index or enrolment date
 - Hospitalizations
 - ED Visits
 - Clinic Visits

Once the data have been reconciled, distributions of the candidate variables will be assessed. Variables will be excluded from the analysis if none of the subjects from the prospective arm have the characteristic or there is little variability. To maximize the number of subjects from the prospective arm, when discrete variables have missing data, an “unknown” category will be created. With respect to missing data for continuous variables, the population mean will be imputed.

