- A logistic regression model will be developed to estimate a propensity score for each subject. The model will include candidate variables (defined in Section 3.5.2 Step 2: Produce Candidate Pool for Historical Cohort). The dependent variable will be binary and indicate either prospective patient or historical control patient. Backwards stepwise selection will be implemented with alpha level of 0.1 or 0.20 to identify predictor variables of receiving Furoscix (prospective subject vs. historical control). The final model including candidate variables identified from backwards stepwise selection will be used to generate a predicated probability (propensity score of receiving Furoscix) for each subject.
- For treatment arm, the variables will be defined at time zero (enrollment/ED visit); for control patients, the variables will be defined at index as a possible match.
- Once final matches are identified, to assess balance in confounding variables between cases and controls, for each of the candidate variables included in the propensity score modeling, effect sizes (normalized difference between cases and controls) will be calculated based on the differences between the matched pairs. An effect size of <0.20 will be deemed acceptable.
- Control patients' data were weighted based on the number of controls within each matched treatment arm patient set. For instance, if a control patient was part of a set with 1 other control patient, each control patient in that set was weighted 0.50 (1 divided by the set count 2).
- In addition to the effect size evaluation, the baseline characteristics, i.e. all initial candidate variables for propensity model, between the two cohorts will be compared statistically and any variable difference with a p value of <0.1 will be identified.

Analyses, whether they be interim or final, will be conducted sequentially using the SEQTEST procedure in SAS, which has been specified elsewhere (SAS Institute, 2009). Briefly, The SEQTEST procedure performs interim and final

analyses by comparing test statistics with corresponding boundary values obtained with the SEQDESIGN procedure. If the information levels for the test statistics do not match the information levels obtained with the SEQDESIGN procedure, the SEQTEST procedure modifies the original boundary values to adjust for actual (observed) information levels.

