3.5.6. Secondary Outcomes

Outcomes for the endpoints related to healthcare utilization (i.e., Secondary Endpoints 1-4) will be evaluated by appropriate statistical test dependent on the distribution of the outcome. Health-related quality of life outcomes will be evaluated for the Furoscix cohort only and will descriptively compare KCCQ-12 questionnaire responses at Day 0 versus Day 30. Change in BNP or NT-proBNP will be evaluated for the Furoscix cohort only and will descriptively compare values obtained at Day 0 versus Day 30. Subject and/or caregiver satisfaction with Furoscix Infusor will be descriptive.

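### The primary cost comparison has no covariate-adjusted estimate, even as a sensitivity analysis, so baseline imbalance that the matching tolerates is never corrected in the reported saving

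*SAP*

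**What the plan says.** SAP 3.5.1 gives the primary analysis, for overall and for HF-related 30-day cost: "Comparison of these data between the matched (paired) cohorts will be conducted via a t-test or a Wilcoxon signed-rank test", chosen by the distribution of the data. Protocol 8.3.1 and the protocol synopsis say the same. SAP 3.5.4 states the target as a difference in mean cost.

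SAP 3.5.3 lists candidate variables for the propensity score: age, sex, region, medications, comorbidities including CKD stage, and "Baseline resource utilization (All-cause and HF-related) in the 6 months prior to index or enrolment date" (hospitalizations, ED visits, clinic visits). Only variables that can be defined consistently in the trial and claims data are kept.

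SAP 3.5.5 then sets the matching:

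- The propensity model predicts trial membership and is reduced by backward selection at 0.1 or 0.20.
- Matches must lie within 0.01 on the score, agree on sex and be within 5 years of age. One to four controls are matched per Furoscix subject.
- No Furoscix subject is to be lost for want of a match.
- On balance: "An effect size of <0.20 will be deemed acceptable". Baseline differences with p<0.1 are to be identified. Neither check has a stated consequence for the cost analysis.

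The only further final analysis named for this comparison is a higher matching ratio, up to 1:10.

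**The concern.** Prior hospitalizations and visits are the baseline counterparts of the events that SAP 3.5.3.1 prices into 30-day cost, so they are plausible predictors of the outcome. The plan relies on matching alone to balance them, and the matching leaves three gaps. The propensity model is built to predict trial membership rather than cost, so selection can remove a variable that matters for cost. The balance criterion tolerates up to 0.20 SD on each variable. Nothing is prescribed when the criterion fails.

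In a randomized trial a chance imbalance of this kind averages out over repetitions. Here assignment is not randomized (Protocol 5.3.1), and a systematic imbalance goes into the reported saving as bias. That bias does not shrink as enrolment moves from 34 toward 75, while the standard error does, so its effect on the test grows.

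**Working it through.** **Inputs.** Control mean $8,600, treated mean $6,500, difference $2,100, SD $3,045, 34 evaluable per group, 80% power (SAP 3.5.2, 3.5.4); two-sided alpha 0.05 (SAP 3.3.3); tolerated imbalance 0.20 and matching 1:1 to 4:1 (SAP 3.5.5). The documents give no correlation r between a baseline variable and cost. It is an assumption throughout, shown as a range.

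**The plan's own figure.** A two-sample t-test with these inputs needs 33.99, so 34 per group, and has 80.0% power at 34. The stated N reproduces as an unpaired, unadjusted calculation.

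**Bias from one covariate.** Bias = imbalance × r × SD = 0.20 × r × $3,045.

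| r | Bias | Share of $2,100 |
|---|---|---|
| 0.1 | $61 | 2.9% |
| 0.2 | $122 | 5.8% |
| 0.3 | $183 | 8.7% |
| 0.4 | $244 | 11.6% |
| 0.5 | $304 | 14.5% |

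**Check by simulation.** This used 34 pairs, a true saving of $2,100, and Furoscix subjects 0.20 SD lower on one covariate that raises cost. The unadjusted paired estimate averaged $2,215, $2,272 and $2,419 for r = 0.2, 0.3 and 0.5. A pair-difference regression on the covariate averaged $2,090, $2,092 and $2,104. With the imbalance reversed, the unadjusted saving was understated instead ($1,997, $1,926, $1,791).

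**Effect on the test.** Under no true difference the standard error at 34 per group is 3,045 × √(2/34) = $739. A single fixed-sample test at 1.96 then has type I error 5.3%, 5.7% and 7.0% for r = 0.2, 0.3 and 0.5. At 75 per group the figures are 5.7%, 6.6% and 9.4%.

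**Several covariates.** Five independent covariates, each 0.20 SD out in the same direction and jointly explaining 10% to 30% of cost variance, give 5 × 0.20 × √(R²/5) × $3,045 = $431 to $746 (21% to 36% of $2,100).

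**Would the balance checks catch it?** A two-sample t-test reaches p<0.1 only at about 0.40 SD with 34 against 34, and about 0.32 SD with 34 against 136. A difference just under 0.20 passes both checks. Nor is 0.20 a ceiling. If matching balanced a variable no better than random allocation (an assumption), its difference would exceed 0.20 with probability about 41% at 34 against 34 and 30% at 34 against 136.

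**Precision.** Adjusted SD = SD × √(1 − r²). Two-sample t power with 34 Furoscix subjects, treating controls as independent:

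| Ratio | Unadjusted | r = 0.3 | r = 0.5 |
|---|---|---|---|
| 1:1 | 80.0% | 83.6% | 89.9% |
| 4:1 | 94.7% | 96.3% | 98.5% |

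The gain is 3.6 or 9.9 points at 1:1, and 1.6 or 3.8 points at 4:1. In the paired simulation at r = 0.2 there was none (79.4% unadjusted, 79.3% adjusted).

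**Small interim.** SAP 3.5.5 also tests at N=10. With 10 pairs, four normal covariates and no effect, a matched-set clustered statistic read on the Z scale rejects about 9% of the time at 1.96. At an illustrative strict boundary of 3.6 it rejects about 1%, against a nominal 0.03%. A paired t-test with its own t reference rejects 4.8% at the 5% level.

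**The case against.** Matching followed by a paired comparison is a recognised analysis, and outcome regression on top of it can be called an enhancement. Four stronger readings are tempting, and the documents do not support them.

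- A reader might take the tolerance to mean that 0.20 SD of cost, or $609, enters the saving. It is 0.20 SD of a covariate and reaches cost only after scaling by r.
- A reader might infer that the baseline variables serve only the propensity model. Age and sex are also direct matching criteria, the claims pool excludes CKD stage 4/5, ESRD and renal failure, and the same variables feed the Cox model in SAP 3.6.1. Adjusting for age and sex would add little.
- A reader might conclude that the unadjusted test costs about 10 points of power. That needs r = 0.5 and 1:1 matching; the plan allows 4:1, where the gain is about 4 points, and pairing may already recover part of it.
- A reader might assume that baseline counts are available for adjustment. SAP 3.5.3 describes the pool by binary indicators and keeps only variables that can be reconciled, so only yes/no versions may exist.

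Two further limits stand. No direction of imbalance can be inferred, so the bias could overstate or understate the saving. The SD of $3,045 describes hospital cost, whereas the endpoint sums benchmark costs per event, so its SD may differ.

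For the utilization endpoints, SAP 3.5.6 says that they "will be evaluated by appropriate statistical test dependent on the distribution of the outcome". That leaves room for count regression, so the point is confined to cost. None of this supplies a correction for tolerated imbalance or an adjusted cost estimate.

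**Conclusion.** The point holds as a gap in the primary analysis, and bias is the main reason to act. For one covariate at the tolerated limit the saving moves by about $61 to $304 (3% to 14.5% of $2,100) for r from 0.1 to 0.5. It moves more if several prognostic variables lean the same way. The formula and the absence of an adjusted estimate are firm. The value of r, the common direction across variables and the transfer of the $3,045 SD to benchmark-based cost are assumptions, so the dollar amounts are illustrative. Prior utilization and comorbidities offer most of the gain. Precision is a secondary benefit: about 4 to 10 points of power at 1:1 and about 2 to 4 at 4:1 for r of 0.3 to 0.5, and negligible at r of 0.2 or below.

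**What to change.** In SAP 3.5.1 and 3.5.5, and in Protocol 8.3.1, pre-specify for the N=34 and later analyses a linear regression of 30-day cost on arm plus a short list of reconciled baseline variables, fitted separately for overall and HF-related cost. An example list is prior six-month HF hospitalization, prior six-month HF ED visit and CKD stage, as counts or indicators, whichever can be reconciled. Fit it on the matched set with the existing control weights and standard errors clustered on matched set. Apply a small-sample, t-based correction before the result is compared with the SEQTEST boundaries. Report the adjusted difference as the primary estimate, or at minimum as a key sensitivity estimate, beside the unadjusted paired test.

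At the N=10 interim keep the unadjusted paired test, or use at most one covariate, because of the inflation shown above.

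The change needs SAP and protocol wording and a few lines of SAS. It uses no data beyond the variables that SAP 3.5.3 already sets out to reconcile, and missing values there already have a rule. It uses up a few degrees of freedom and relies on a linear covariate term. It cannot remove confounding by variables absent from claims, such as laboratory values.

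### The primary test may switch to a Wilcoxon signed-rank test, which tests the SAP's mean-cost null only if the pair differences are symmetric

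*SAP*

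**What the plan says.** SAP 3.5.1 states that the comparison of the matched cohorts "will be conducted via a t-test or a Wilcoxon signed-rank test depending on the distribution of the data". Protocol 8.3.1 repeats this ("will be conducted via a t-test or a Wilcoxon signed-rank test depending on distribution of data"), as does the statistical part of the synopsis. None of them gives a normality test, a threshold or a time at which the choice is made.

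SAP 3.5.4 sets the hypothesis on arithmetic means. It begins "Assume that the total 30-day HF-related direct medical costs are normally distributed with means" mu_e and mu_c, and takes H0: theta = mu_e - mu_c = 0. In words this is the "null hypothesis being that there is no difference in 30-day HF-related direct medical costs between the Furoscix Infusor and historical control arms". The design inputs are on the same scale: "The boundary values will be estimated based on a difference of" $2,100, that is, $8,600 down to $6,500 with SD $3,045. SAP 3.3.3 sets a two-sided 5% test.

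SAP 3.3.5 (step 1) asks for the test statistic to be fixed before boundaries are computed. SAP 3.5.5 plans looks at N=10 and N=34, with more if needed, and passes the statistics to SEQTEST.

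**The concern.** The signed-rank test addresses symmetry of the pair differences about zero, that is, their pseudo-median. It agrees with theta = 0 only if those differences are symmetric. Costs in this design may well not be. Every control enters through a 1 to 3 day HF admission (SAP 3.5.3). A Furoscix subject is treated outside the hospital and becomes expensive mainly if later admitted. Many modest costs and a few large ones can have the same mean as the control arm and still lie below it in most pairs.

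The economic question is mean cost per patient. If the fallback is used, the primary p-value may belong to a different quantity from the saving being reported. Because no selection rule is given and several looks are planned, the statistic could also change between looks.

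**Working it through.** **1. The plan's own figure is a comparison of means.** Inputs from SAP 3.5.2: difference $2,100, SD $3,045, 80% power, 5% level (two-sided per SAP 3.3.3).

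n per group = 2 × [SD × (1.960 + 0.842) / difference]² = 2 × (1.45 × 2.802)² = 33.0 before rounding up, so 34. The two-sample t calculation gives 33.99, so 34, with 80.0% power. A one-sided test would need 26. The stated 34 is therefore reproduced as a two-sided test of a mean difference.

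**2. Equal means do not imply a centred pair difference.** Suppose 80% of Furoscix subjects cost around $5,000 and 20% around $23,000. The mean is 0.8 × 5,000 + 0.2 × 23,000 = 4,000 + 4,600 = $8,600, the control mean. Against gamma controls (mean $8,600, SD $3,045), about 70% of pair differences are below zero and their median is about -$2,350, although their mean is zero.

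**3. Rejection rates with both means at $8,600.** Pairs matched 1:1, control gamma with SD $3,045, 20,000 trials per row, one fixed two-sided 5% test. The Furoscix shapes are assumptions. Each entry sums rejections in both directions.

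| Furoscix cost shape (mean $8,600) | N=34 signed-rank | N=34 t-test | N=75 signed-rank | N=75 t-test |
|---|---|---|---|---|
| Same gamma as control | 4.8% | 4.9% | 4.8% | 4.9% |
| Lognormal, SD $3,045 | 4.6% | 4.8% | 5.1% | 4.8% |
| 70% near $6,500, 30% near $13,500 | 7.8% | 5.2% | 11.0% | 5.2% |
| Lognormal, SD $6,090 | 9.8% | 5.7% | 15.5% | 5.2% |
| 70% near $5,000, 30% near $17,000 | 13.1% | 5.7% | 22.2% | 5.3% |
| Lognormal, SD $8,600 | 18.4% | 7.9% | 33.1% | 6.7% |
| 80% near $5,000, 20% near $23,000 | 31.5% | 7.2% | 56.3% | 6.0% |
| Lognormal, SD $12,900 | 33.4% | 10.9% | 61.8% | 9.3% |
| 90% near $6,500, 10% near $27,500 | 38.3% | 9.7% | 68.4% | 6.8% |

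For example, in the lognormal SD $8,600 row the signed-rank test at N=34 declares a saving in 18.3% of trials and an excess cost in 0.1%. Further simulations over other mild and strong shapes gave 6-11% and 19-36% at N=34, and 34-65% for strong skew at N=75.

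Under skew, the signed-rank rate rises with N while the t-test rate falls or stays near nominal. That is the mark of a different target rather than of small-sample error. Nearly all rejections here favour Furoscix because the skew was placed in that arm; skew in the control arm would act the other way.

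**4. Under the SAP's pricing.** SAP 3.5.3.1 builds each patient's cost by adding standard prices for events, so the continuous shapes above are only stand-ins. With assumed Poisson event counts, an ED visit at $1,200, a clinic visit at $200 and N=34 at 1:1:

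- All admissions at $8,600 (control readmission rate 0.10-0.25): equal means need 0.93-1.08 admissions per Furoscix subject. Signed-rank rejects 5-6%, the t-test 5%.
- Later admissions at $12,000-20,000 (control readmission rate 0.15): equal means need 0.5-0.7 admissions per subject. Signed-rank rejects 7-24%, the t-test 5-6%.

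Other assumed benchmark prices took the signed-rank rate up to 36%, and in one case (14%) the rejections favoured control.

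**The case against.** The strongest reply is that the large error rates come from cost shapes the documents do not contain. The expected overdispersion (Protocol 8.1) is given as a reason for sample-size re-estimation; it states neither skewness nor a difference in shape between arms. Under benchmark pricing, equal means require many Furoscix admissions. At 0.30 admissions per subject, all at $8,600, both tests reject in at least 99% of trials, and the choice would not change the conclusion. This stands as a limit on size. A reader might infer that this trial carries a one-in-three chance of a false saving, or that the error always favours Furoscix. The documents support neither.

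A second reply is that SAP 3.3.5 (step 6) already calls for an estimate, confidence limits and a p-value, and that SEQTEST works on theta. That does not remove the switch. SEQTEST compares whatever statistic it is given with the boundaries, and no section says which statistic is used once the signed-rank test has been chosen.

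A third reply is that a mean-based test is not clean either. This is correct. With a lognormal Furoscix arm at N=34 (1,000 trials, nominal 5%), rejection was 9.6% for the t-test, 9.7% for a sign-flip permutation-t, 9.6% for a bootstrap-t and 10.6% for a percentile bootstrap interval. At N=10 the first three ran at 9-10% and the percentile bootstrap at 14%. At N=10 the t-test and the signed-rank test are also alike: 8.9% and 8.7% declare a saving in the lognormal SD $8,600 case. The clear gain from a mean-based test is at N=34 and above.

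**Conclusion.** The inconsistency holds on the text alone: hypothesis, effect size and boundaries concern mean cost, and the permitted fallback does not unless the pair differences are symmetric. With equal means at N=34, the simulated two-sided error of the signed-rank test is about 5% for identical shapes at 1:1, 6-11% for mild skew and 19-36% for strong skew in the Furoscix arm. The t-test is at about 5-8%, and reaches 10-11% only in the two most extreme shapes tabulated. The signed-rank error grows with N.

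These sizes rest on assumed Furoscix distributions and on one fixed 5% test rather than the O'Brien-Fleming boundaries. Those boundaries change the critical values but not the quantity being tested. The figures show what the rule permits and are not a forecast for this trial. The stronger conclusion, that the switch will produce a false saving here, would need the Furoscix cost distribution, which the documents do not give.

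**What to change.** In SAP 3.5.1, Protocol 8.3.1 and the synopsis, delete the clause that makes the test depend on how the data are distributed. Then:

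- Name one primary test of the mean matched-set difference, d_i = cost of subject i minus the weighted mean cost of its matched controls, using the weights already in SAP 3.5.5.
- Feed that statistic to SEQTEST at every look, and report the mean difference with its confidence interval.
- Keep the signed-rank test as a sensitivity analysis only.
- If a bootstrap-t or permutation reference is used, say so in advance, and state that any mean-based test remains somewhat anti-conservative under strong skew at N=10 to 34.

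The cost is wording in two documents and a few lines of code. The stated 34 per group, itself a comparison of means, is unaffected. As a paired t-test, the same inputs need 35 pairs at zero within-pair correlation and 19 at 0.5 (correlations assumed). The price is a somewhat wider interval and less power when tails are heavy.
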